5.2.6 Treatment Compliance

No analysis is planned.

5.3 Data Analysis General Considerations

5.3.1 Pooling of Centers

Subjects from all centers will be pooled for all analyses.

5.3.2 Adjustments for Covariates

Not applicable.

5.3.3 Multiple Comparisons/Multiplicity

Not applicable.

5.3.4 Examination of Subgroups

Not applicable.

5.3.5 Handling of Missing Data, Dropouts, and Outliers

Subjects that drop out and are unevaluable for DLT evaluation would be replaced per protocol.

No imputation for missing data will be performed in general, unless it is indicated for specific considerations. The imputation rules for partial date in order to derive a variable for disease characteristics will be specified in the study analysis dataset specification. For incomplete dates involving efficacy and safety data such as AEs, concomitant medications, laboratory values, vital signs and ECGs, a conservative imputation will be used for calculation. The imputation rules will be specified in study analysis dataset specification with more details. For endpoints that determine the percentage of responders, subjects with unknown response will be treated as non-responders.

Eisai Confidential Page 13 of 30

5.3.6 Other Considerations

Not applicable.

5.4 Efficacy Analyses

Tumors are evaluated every 2 cycles (8 weeks) by investigator's assessment based on RECIST 1.1. Assessments will continue until radiological disease progression or initiation of new anti-cancer therapy. Detailed BOR derivation rule is included in Appendix 13.1. Detailed PFS censoring is included in Appendix 13.2.

All efficacy parameters will be summarized descriptively for either RES or FAS, or both.

5.4.1 Primary Efficacy Analyses

Not applicable.

5.4.2 Secondary Efficacy Analyses

ORR and CBR will be summarized by treatment groups, and exact 95% CIs will be provided using the method of Clopper and Pearson (1934).

In addition, waterfall plot of best percentage change of sum of diameters in target lesion will be provided for RES subjects

PFS analysis will follow the FDA censoring rule guidance: progression date is assigned to the earliest date when any RECIST 1.1-defined disease progression is observed without missing more than 1 adequate radiologic assessments. Details are included in Appendix 13.2. The distribution of PFS will be estimated using Kaplan-Meier methodology. Median PFS and the corresponding 2-sided 95% CIs (Brookmeyer and Crowley, 1982) will be summarized by treatment groups. The PFS rate at 3-month, 6-month, and 9-month and 12-month will be estimated using the Kaplan-Meier Method and the corresponding 2-sided 95% CIs will be summarized. In addition, Kaplan-Meier plots of PFS will be presented.

DOR will be calculated for subjects achieving a best overall response of confirmed PR+CR. If there are ≥7 subjects with confirmed responses, the median of DOR will be estimated using Kaplan-Meier methodology; median DOR and the corresponding 2-sided 95% CI will be presented by treatment groups on RES. The same logics in censoring rules as those for PFS analysis will be applied. If there are <7 subjects with confirmed responses, DOR will be listed.

OS will be censored at the last alive date or data cutoff date, whichever comes first. The distribution of OS will be estimated using Kaplan-Meier methodology. Median survival time and the corresponding 95% CI, survival rates at 6, 12, 18, 24 months, and corresponding 95% CIs will be estimated using Kaplan-Meier method. The analysis will be presented by treatment groups.

Eisai Confidential Page 14 of 30

5.4.3 Other Efficacy Analyses

Not applicable.

5.5 Pharmacokinetic, Pharmacodynamic, Pharmacogenomic, and Other Biomarker Analyses

This section describes statistical analysis for non-compartmental analysis (NCA)-based PK parameters, PD parameters, pharmacogenomic and other biomarkers if applicable. Modeling such as population PK or PK/PD is not included in this SAP and if conducted, will be described in separate analysis plans.

5.5.1 Pharmacokinetic Analyses

Plasma concentrations

The plasma concentrations of palbociclib and H3B-6545 will be summarized using summary statistics (n, mean, standard deviation, median, minimum and maximum) by cohort, day and nominal sampling time points. The following figures will be displayed.

- 1. Linear and semi-logarithmic plots of mean plasma concentration-time profiles
- The time after dose (nominal time) will be plotted on the X axis and mean plasma concentrations of H3B-6545 and palbociclib will be plotted on the Y axis with standard deviation by cohort and day.
- 2. Linear and semi-logarithmic plots of individual plasma concentration-time profiles
- The time after dose (actual time) will be plotted on the X axis and individual plasma concentrations of H3B-6545 and palbociclib will be plotted on the Y axis by cohort and day.

PK parameters

The PK parameters of palbociclib and H3B-6545 will include, as applicable, maximum observed concentration (C_{max}), time at which the highest drug concentration occurs (t_{max}), AUC from zero time to time of last quantifiable concentration (AUC_(0-t)), AUC from zero time to 24 hours (AUC_(0-24h)), and apparent total clearance following oral administration (CL/F) will be summarized using summary statistics (n, mean, standard deviation, geometric mean [CV%], median, minimum and maximum) by cohort and day. Mean, standard deviation and geometric mean (CV%) are not required for t_{max}. PK parameters will be derived according to Eisai non-compartmental pharmacokinetic Analysis Manual (302-104.01-MNL). To calculate PK parameters, actual sampling time will be used.

The DDI effect will be estimated as a ratio of exposure index (C_{max}, AUC_(0-24h), and C₂₄) in the following way in the dose escalation part: ratio of palbociclib exposure on Cycle 1 Day 21/palbociclib exposure on Cycle 1 Day 8 for potential effect of H3B-6545 on palbociclib

Eisai Confidential Page 15 of 30

and ratio of H3B-6545 exposure on Cycle 1 Day 21/H3B-6545 exposure on Cycle 1 Day 28 for potential effect of palbociclib on H3B-6545. This ratio will be summarized using summary statistics (n, mean, standard deviation, CV%, median, minimum and maximum) by cohort.

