Grade 3 (symptomatic, intervention indicated)	Withhold palbociclib until (a) symptoms resolve and (b) heart rate is \geq 50 bpm; resume drug at the next lower dose	Withhold drug until (a) symptoms resolve and (b) heart rate is \geq 50 bpm; resume drug at the next lower dose
Grade 4 (Life-threatening consequences; urgent intervention indicated)	Withhold palbociclib until (a) symptoms resolve and (b) heart rate is \geq 50 bpm; resume drug at the next lower dose	Discontinue drug
QTcF prolongation		-
Grade 1 (average: 450 – 480 ms)	No dose adjustment is required	No dose adjustment is required

Grade 2	No dose adjustment is required	No dose adjustment is required
(average: 481 – 500 ms)		Repeat assessment after 1 week; if the average is still between 481 and 500 mg, decrease to the next lower dose
Grade 3 (average: ≥501 ms; >60 ms change from baseline)	Withhold drug until average is <480 ms and <60 ms change from baseline; resume at the next lower dose	Withhold drug until average is <480 ms and <60 ms change from baseline; resume at the next lower dose
Grade 4 (Torsade de pointes; polymorphic ventricular tachycardia; signs/symptoms of serious arrhythmia)	Discontinue drug	Discontinue drug
Other		
Grade 1 or 2	No dose adjustment is required	No dose adjustment is required
Grade 3 or 4 (if persisting despite optimal medical care)	Withhold palbociclib until symptoms resolve to Grade ≤2; resume drug at the next lower dose	Withhold drug until symptoms resolve to Grade ≤ 2 ; resume drug at the next lower dose

CTCAE = Common Terminology Criteria for Adverse Events; QTcF = QT interval corrected for heart rate using Fridericia's formula.

Monitor subjects for pulmonary symptoms indicative of ILD/pneumonitis (eg, hypoxia, cough, dyspnea). In patients who have new or worsening respiratory symptoms and are suspected to have developed ILD/pneumonitis, interrupt palbociclib immediately and evaluate the subject. Permanently discontinue palbociclib in subjects with severe ILD or pneumonitis.

Dose modifications for use with strong CYP3A inhibitors

Avoid concomitant use of strong CYP3A inhibitors and consider an alternative concomitant medication with no or minimal CYP3A inhibition. If patients must be co-administered a strong CYP3A inhibitor:

- Reduce the palbociclib dose to 75 mg QD
- Reduce the H3B-6545 dose to 150 mg QD

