9.8.1.7 Pharmacokinetic, Pharmacodynamic, Pharmacogenomic, and Other Biomarker Analyses

9.8.1.7.1 PHARMACOKINETIC ANALYSES

The plasma concentrations of palbociclib and H3B-6545 will be presented by dose level and day, as the number of subjects with data, geometric mean, mean, standard deviation (SD), median, minimum, and maximum values by nominal sampling timepoint. The PK parameters will include, as applicable, C_{max} (maximum observed plasma concentration), T_{max} (time of the maximum observed plasma concentration), AUC_{0-24} (AUC from zero time to 24 hours), AUC_{0-t} (AUC from zero time to last measurable concentration), AUC_{0-inf} (AUC from zero time to infinity), percentage of AUC that is due to extrapolation from the last measurable concentration to infinity (% AUC_{Extrap}), apparent terminal disposition rate constant (λ_z), apparent plasma terminal elimination half-life, apparent total plasma clearance (CL/F), and apparent volume of distribution (V/F) and will be summarized by cohorts and day, with the number of measurements, number of non-missing data, the number of subjects, geometric mean (CV%), mean, SD, median, minimum, and maximum.

The DDI effect will be estimated as a ratio of exposure index (C_{max} , AUC₀₋₂₄, and C_{24}) in the following way in the dose escalation cohort: ratio of palbociclib exposure on Day 21/palbociclib exposure on Day 8 for potential effect of H3B-6545 on palbociclib and ratio of H3B-6545 exposure on Day 21/H3B-6545 exposure on Day 28 for potential effect of palbociclib on H3B-6545. This ratio will be summarized by cohorts with the number of subjects, geometric mean (CV%), mean, SD, median, minimum, and maximum.

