7 CHANGES IN THE PLANNED ANALYSES

If the SAP needs to be revised after the study starts, the sponsor will determine how the revision impacts the study and how the revision should be implemented. The details of the revision will be documented and described in the clinical study report.

Major changes of the analysis plan between SAP v1.0 to v2.0 are as follows:

- Specified new timing of primary analysis according to Protocol Amendment 04 (29 Aug 2022).
- Clarified summary of previous anti-cancer therapies and subgroup analysis
- Geometric mean (CV%) was deleted from the summary statistics for plasma concentrations of palbociclib and H3B-6545.
- The PK parameters calculated based on the terminal phase rate constant (λ_z) ($t_{1/2}$ and V_z/F) were deleted from the analysis plan, because the blood sampling time points were not enough to calculate λ_z accurately.
- Definitions and conventions for PK data handling were added.

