Pharmacokinetic assessments: The lower limit of quantification (LLOQ) in plasma is 1.00 ng/mL for palbociclib and 1.00 ng/mL for H3B-6545, respectively. While calculating PK parameters, below lower quantification (BLQ) values will be handled according to 302-104.01-MNL. When developing individual concentration-time profiles, BLQ values will be handled according to 302-104.01-MNL. The handling of anomalous concentration values will follow 302-104.01-MNL. When presenting individual/raw (raw, hereafter) values and summary statistics, the following rule will be applied for drug concentrations and PK parameters.

Typical variable	Unit	N	Digit rule	Raw Minimum Maximum	Mean Median	Standard deviation	Geometric Mean	CV (%)
Plasma concentration	ng/mL	X	Significant digits	3	3	3	_	ı
C _{max}	ng/mL	X	Significant digits	3	3	3	3	3
t _{max}	h	X	Fixed decimal places	2	2	ı	_	ı
AUC	ng•h/mL	X	Significant digits	3	3	3	3	3
CL/F	L/h	X	Significant digits	3	3	3	3	3
Ratio of exposure index	No units	X	Significant digits	3	3	3	3	3

Eisai Confidential Page 23 of 30

Individual pharmacokinetic data: The following data will not be included in the calculation of summary statistics.

- Plasma concentration data at predose if the blood samples are collected after administration
- PK data (plasma concentrations and PK parameters) in a patient with any dose modification (increase, reduction, or interruption) within 3 days prior to the blood sampling.
 - ie, The following PK data will not be included in the calculation of summary statistics;
 - PK data of palbociclib from a patient with dose modification in palbociclib from C1D5 to C1D8
 - PK data of palbociclib and H3B-6545 from a patient with dose modification in palbociclib or H3B-6545 from C1D18 to C1D21
 - PK data of H3B-6545 from a patient with dose modification in H3B-6545 from C1D25 to C1D28
- Dosing and sampling date/time are missing

The following case will be determined individually:

• Significant deviation from the allowance of PK blood sampling schedule

Further definitions and conventions for data handling will be presented in "Programming Specifications".

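### SAP 5.5.1 omits the geometric mean of the drug-interaction ratio that the protocol and SAP Section 8 provide for, and the Section 8 exclusion windows can leave two different doses in one ratio (minor)

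*SAP*

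**What the plan says.** **The ratio.** Protocol 9.8.1.7.1 and SAP 5.5.1 define it in the same way for three exposure indices: Cmax, AUC(0-24h) and C24. For palbociclib it is Cycle 1 Day 21 over Day 8. For H3B-6545 it is Day 21 over Day 28. SAP 5.1.2 names it among the secondary endpoints.

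**How it is summarized.** The protocol says: "This ratio will be summarized by cohorts with the number of subjects, geometric mean (CV%), mean, SD, median, minimum, and maximum". SAP 5.5.1 says: "This ratio will be summarized using summary statistics (n, mean, standard deviation, CV%, median, minimum and maximum) by cohort". The SAP Section 8 digit table has a row "Ratio of exposure index" with three significant digits under both Geometric Mean and CV (%). The same table puts dashes in those two columns for plasma concentration and for tmax. The SAP Section 7 change log records one deletion of this kind, and it concerns concentrations: "Geometric mean (CV%) was deleted from the summary statistics for plasma concentrations of palbociclib and H3B-6545".

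**Which PK data are excluded.** SAP Section 8 drops data from a subject with "any dose modification (increase, reduction, or interruption) within 3 days prior to the blood sampling". It spells this out as palbociclib changes on Days 5 to 8 for the Day 8 data, changes in either drug on Days 18 to 21 for the Day 21 data, and, for Day 28, "PK data of H3B-6545 from a patient with dose modification in H3B-6545 from C1D25 to C1D28". Neither document requires the same dose on both days of a ratio, and neither mentions dose normalization.

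**The concern.** A ratio of exposures is a multiplicative quantity. A doubling and a halving should cancel, and they do on the geometric scale: the geometric mean of 2 and 0.5 is 1.00, while their arithmetic mean is 1.25. If programmers follow 5.5.1 as written, the only mean reported tends to sit above 1 for both drugs even when neither affects the other. The CV% left in that sentence is also ambiguous. The protocol synopsis bases the CV of PK parameters on untransformed data, whereas Protocol 9.8.1.7.1 and the SAP parameter summaries attach CV% to the geometric mean.

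The second matter is independent of the first. The ratio is meant to isolate the effect of one drug on the other, and the staggered Cycle 1 schedule in Protocol 7.3 was built to give the single-drug and combination days. If a subject's dose changes between the two days, the ratio moves for a reason unrelated to interaction. A palbociclib reduction lowers it, and an H3B-6545 reduction raises it. Restoring the geometric mean does not cure that.

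**Working it through.** The documents give no figure to reproduce: the analysis is descriptive, and no CV or expected ratio is stated.

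**1. Arithmetic mean when there is no interaction.** Assumptions: log-normal exposures, true ratio 1, CV 20 to 50%, six subjects per cohort (Protocol 9.1).

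- If the CV is the within-subject CV on each occasion, Var(log ratio) = 2 ln(1 + CV²), and the expected arithmetic mean is 1 + CV².
- If the CV is that of the ratio itself, Var(log ratio) = ln(1 + CV²), and the expected arithmetic mean is √(1 + CV²).
- The expected geometric mean of six is exp(Var/12).
- The expected median of six comes from simulation (400,000 draws).

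| Assumed CV | Per occasion: arithmetic | median | geometric | CV of ratio: arithmetic | median | geometric |
|---|---|---|---|---|---|---|
| 20% | 1.04 | 1.01 | 1.01 | 1.02 | 1.01 | 1.00 |
| 30% | 1.09 | 1.03 | 1.01 | 1.04 | 1.01 | 1.01 |
| 40% | 1.16 | 1.04 | 1.02 | 1.08 | 1.02 | 1.01 |
| 50% | 1.25 | 1.07 | 1.04 | 1.12 | 1.03 | 1.02 |

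The arithmetic mean is the outlier. The median, which 5.5.1 keeps, stays within about 0.03 of the geometric mean.

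**2. Days covered by no window.**

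- Palbociclib, Day 8 to Day 21: changes on Days 18 to 21 are excluded, so Days 9 to 17 (nine days) are open.
- H3B-6545, Day 21 to Day 28: changes on Days 25 to 28 are excluded, so Days 22 to 24 (three days) are open.

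**3. Can the protocol put a change there?**

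- H3B-6545: for Grade 2 QTcF, Protocol Table 6 says "Repeat assessment after 1 week; if the average is still between 481 and 500 mg, decrease to the next lower dose" (the unit is evidently milliseconds). No hold is involved. An ECG is scheduled on Day 15, and 15 + 7 = Day 22, which is outside both H3B-6545 windows.
- Palbociclib: Table 5 holds the drug for Grade 4 hematologic toxicity and resumes it at a lower dose. A blood count is scheduled on Day 8. A hold from Day 9 lasting the 7-day median duration that Protocol 9.5 quotes for Grade ≥3 neutropenia ends with resumption on Day 16, inside the open interval.

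**4. Size of a mismatch.** Assume exposure proportional to dose, no interaction and, for illustration only, one subject in six affected. With that subject's ratio equal to x, the cohort geometric mean is x^(1/6) and the arithmetic mean is (5 + x)/6. The dose steps are those in Protocol 9.5.

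| Step between paired days | x | Geometric mean | Arithmetic mean | Shift in typical cohort median |
|---|---|---|---|---|
| Palbociclib 125 to 100 mg | 100/125 = 0.80 | 0.963 | 0.967 | about −3 to −4% |
| H3B-6545 450 to 300 mg | 450/300 = 1.50 | 1.070 | 1.083 | about +5 to +7% |
| H3B-6545 300 to 150 mg | 300/150 = 2.00 | 1.122 | 1.167 | about +5 to +11% |

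The median shifts are simulated over both readings of the CV. The median, which softens the first problem, does not remove the second.

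**The case against.** **On the geometric mean.** The SAP as a whole does not abandon it. Section 8 formats a geometric mean for the ratio, and Section 7 records a deletion for concentrations only, so 5.5.1 looks like a drafting slip. This stands. A reader might infer that C24 is left with no geometric summary at all, because it is absent from the 5.5.1 parameter list (which ends "and apparent total clearance following oral administration (CL/F) will be summarized using summary statistics") and concentrations have lost theirs. That is true of the 5.5.1 text alone. C24 is one of the exposure indices that the Section 8 row covers, so the documents support a conflict within the SAP, not an absence. Nor does the protocol rank the geometric mean above the other statistics; calling it the main summary would be a preference.

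**On the dose mismatch.** Several points reduce its likely frequency, and they stand.

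- Grade 3 hematologic toxicity on Day 15 continues palbociclib at the current dose. A Grade 4 hold from Day 15 would usually run into Days 18 to 21 and be excluded. The quoted median time to first neutropenia is 15 days, so a Day 8 trigger should be unusual.
- The QTcF route needs 481 to 500 ms six days after H3B-6545 starts, in subjects screened at 450 ms or below. An ECG is also scheduled on Day 21, and a reduction made that day falls inside the window.
- SAP 5.6.1 lists dosing and dose modifications by subject, so a mismatch in a cohort of six could be seen.
- The PK analysis manual or the Programming Specifications, which are not available here, may already hold a same-dose rule.

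Sampling error is also larger than the artefact. The 95% spread of a six-subject geometric mean, exp(1.96 × SD/√6), is a factor of about 1.17 to 1.71 over the assumed CVs. That supports a low severity. It does not justify keeping a shift whose cause is known and which costs little to remove.

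**Conclusion.** Both parts hold, and both are minor.

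First, SAP 5.5.1 conflicts with Protocol 9.8.1.7.1 and with SAP Section 8 over the geometric mean of the DDI ratio, and Section 7 does not explain it. Followed literally, 5.5.1 gives an arithmetic mean expected at 1.02 to 1.25 under no interaction. This rests on log-normality and an assumed CV of 20 to 50%. The retained median limits the harm, as do the by-day geometric means for Cmax and AUC(0-24h) where the same subjects contribute on both days.

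Second, the stated exclusions leave Days 9 to 17 (palbociclib) and Days 22 to 24 (H3B-6545) open, so one ratio can mix two doses. The illustrative effect on the cohort geometric mean is 0.96, 1.07 or 1.12. The frequency and dose proportionality are assumptions; the gap in the windows is not.

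A reader might go further and infer that dose selection is at risk. The documents do not support that. DLT counting does not use the ratio, no threshold or test is attached to it, and SAP 3.2 says no expansion subjects will be enrolled.

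**What to change.** 1. In SAP 5.5.1, add the geometric mean (CV%) to the sentence on the ratio, for Cmax, AUC(0-24h) and C24, beside the statistics already listed. State whether the CV is the geometric CV or is based on untransformed data. If the omission was intended, say so in Section 7 and correct the Section 8 table.
2. In SAP Section 8, limit each DDI ratio to subjects on the same dose of that drug on both paired PK days, or dose-normalize the exposures and flag those subjects. If the PK manual or the Programming Specifications already contain such a rule, a reference to it in Section 8 is enough.

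The cost is SAP wording and a few lines of code, with no new data. The downside is losing an occasional subject from a cohort of six or, with dose normalization, relying on dose proportionality.

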5.5.2 Pharmacodynamic, Pharmacogenomic, and Other Biomarker Analyses

The baseline tissue biopsies collected will be used to examine potential baseline markers of response. These markers may include but are not limited to ER, PgR, RB, Ki67, HER2, gene expression and DNA mutations (using standard technologies like quantitative polymerase chain reaction, immunohistochemistry, and other appropriate technology) along with global transcription levels (RNA sequencing).

The whole blood samples will be analyzed for evaluation of cell free DNA (cfDNA) as a source of circulating biomarker (DNA mutations). The samples might be used for exploratory analysis for evaluation of response-related and/or safety-related outcomes, as well as for potential use in companion diagnostic and drug development, and would be reported separately if conducted.

Exposure-response with biomarkers and/or other efficacy endpoints might be explored as appropriate with a population PK model-predicted exposure values and if conducted, will be reported separately.

5.6 Safety Analyses

The determination of the MTD and/or RP2D will be based on Dose Evaluable Set that consists of all DLT-evaluable subjects. Subjects not evaluable for DLT assessment will be replaced.

All other safety analyses will be performed on the Safety Analysis Set. Safety data will be summarized on an "as treated" basis using descriptive statistics (eg, n, mean, SD, median, minimum, maximum for continuous variables; numbers and percentages (n [%]) for categorical variables). Safety variables include treatment-emergent adverse events (TEAEs), clinical laboratory parameters, vital signs, and 12-lead ECG results.

Study Day 1 for all safety analyses is defined as the date of the first dose of study drug (H3B-6545 or Palbociclib, whichever is earlier). Safety summary will include post-baseline data during the treatment period (starting from first dose date of study drug to last dose date of study drug + 28 days).

